8.3. Events or Outcomes Qualifying as AEs or SAEs

8.3.1. Clinical laboratory parameters

Abnormal laboratory findings (e.g., clinical chemistry, hematology) or other abnormal assessments (e.g. vital signs) that are judged by the investigator as **clinically significant** will be recorded as AEs or SAEs if they meet the definitions of sections 8.1 and 8.2 respectively. Clinically significant abnormal laboratory findings or other abnormal assessments that are detected during the study or are present at informed consent and significantly worsen during the study will be reported as AEs or SAEs. Clinically significant abnormal laboratory findings or other abnormal assessments that are associated with the disease being studied, and are present at the start of the study but do not worsen, will not be reported as AEs or SAEs. However, if these findings or assessments are judged by the investigator to be more severe than expected considering the subject's condition, then they may be reported as AEs or SAEs.

8.3.2. Pregnancy report

Partner of a subject who become pregnant at any time while the subject is taking part in the study must be reported.

The investigator will record pregnancy information and submit it to ABIVAX or its designee within 24 hours after knowledge of a partner's pregnancy. The partner will also be followed to determine the outcome of the pregnancy, be it full-term or prematurely terminated. Information on the status of the mother and child will be forwarded to ABIVAX or its designee. Follow-up will normally end 6 to 8 weeks following the estimated delivery date.

While pregnancy itself is not considered to be an AE or SAE, any pregnancy complication or elective termination of a pregnancy for medical reasons will be recorded as an SAE. A spontaneous abortion is always considered to be an SAE and will be reported as such.

The time period for collecting pregnancy information is identical to the time period for collecting AEs, as stated in Section 8.4, Time Period, Frequency, and Method of Detecting AEs and SAEs. Pregnancy information is collected from the signing of informed consent to 4 weeks after the last dose.

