3.2. Duration of study participation

From a subject standpoint, the study participation is defined as

- Two to four weeks of screening period;
- Four weeks (Cohorts 1 & 2) or twelve weeks (Cohort 3) as the treatment period (ABX464);
- Follow-up visits at 1 week and 4 weeks after cessation of study medication.

Overall, the minimal study duration will be approximately 70 days and up to 140 days depending on the subject Cohort.

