4.2. Eligibility Criteria

4.2.1. Inclusion Criteria

Subjects will be eligible for inclusion in this study only if ALL of the following criteria apply:

- Males aged 18-65 years;
- Subjects with hematological and biochemical laboratory parameters as follows and within 3 weeks of baseline:
 - Hemoglobin > 9.0 g/dL;
 - Absolute neutrophil count \geq 750/mm³;
 - Platelets \geq 100,000/mm³;
 - Total serum creatinine \leq 1.3 x ULN (upper limit of normal);
 - Creatinine clearance $>$ 50 mL/min by the Cockcroft-Gault equation within 60 days of entry;
 - Total serum bilirubin $<$ 1.5 xULN;
 - Alkaline phosphatase, AST (SGOT) and ALT (SGPT) $<$ 1.5 xULN;
 - Serum lipase less than or equal to 2.0 xULN;
- Subjects should be able and willing to comply with study visits and procedures as per protocol;
- Subjects should understand, sign and date the written voluntary informed consent form at the screening visit prior to any protocol-specific procedures being performed;
- Subjects must agree to use in addition to the condom, a second highly effective method (one for the subject and one for the partner) of contraception (defined as per the CTGF Guidance) during the study and for 3 months after end of study or early termination.

For HIV infected Subjects

- Subjects with a positive HIV-1 serology at any time before the study entry.
- Subjects treated for at least 12 months prior to screening with Dolutegravir or Raltegravir combined with either Tenofovir + Emtricitabine (TDF/FTC) or Abacavir + Lamivudine (ABC/3TC);
- Subjects with HIV plasma viral load \leq 50 copies/mL during the 6 months prior to screening with a maximum of 2 blips \leq 1000 copies during this period;
- Subjects' CD4+ T cells count \geq 250 cells per mm³ at any time since diagnosis;
- Subjects with CD4+ T cells count \geq 600 cells per mm³ at screening.

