- Viral Load, CD4/CD8 count (HIV infected Subjects);
- Perform PK blood sample (at 9AM \pm 1hour);
- Adverse event assessment.

5.3.8. End of Study Visit (D56 for cohort 1&2 or D112 for cohort 3; \pm 7 days)

- Physical examination and vital signs;
- Microbiome specimen collection (swabs);
- Hematology (incl. INR and PT if clinically indicated);
- Biochemistry;
- Urine GC/CT NAAT & Rectal GC/CT NAAT;
- HIV serology (HIV uninfected participants)
- 12 lead ECG;
- Viral Load, CD4/CD8 count (HIV infected Subjects);
- Blood collection for HIV reservoir assessment (HIV infected Subjects) and immuno-evaluation;
- Flexible sigmoidoscopy with collection of rectal biopsies (Cohort 1 and 3 only)
- Perform PK blood sample (at 9AM \pm 1hour);
- Adverse event assessment.

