7.3. Study Discontinuation

All subjects, regardless of the completion or premature discontinuation, should perform the End of Study Visit (EoS) according to the study flow-chart. In case a premature discontinuation this EoS visit should occur within the next two weeks after the last dosing and should include but depending on the subject willingness the PK evaluation and the sigmoidoscopy.

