8.4. Time Period, and Frequency of Detecting AEs and SAEs

All AEs and SAEs occurring from the time a subject consents to participate in the study until 4 weeks after he or she has completed or discontinued the investigational product must be recorded in the subject's eCRF. Importantly, SAEs will have to be reported to ABIVAX or its designee within 24 hours of awareness of an SAE.

Legislative guidance requires also reporting any **related** SAEs to be reported after the subject finished the study if the investigator becomes aware of them.

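### Partner-pregnancy collection stops 4 weeks after the last dose, so new partner pregnancies are not systematically collected for most of the post-treatment contraception period

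*Protocol*

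**What the plan says.** **Collection period.** Protocol section 8.3.2 gives the limit twice. It says "The time period for collecting pregnancy information is identical to the time period for collecting AEs" and then "Pregnancy information is collected from the signing of informed consent to 4 weeks after the last dose". Section 8.4 sets the matching adverse-event (AE) limit: events must be recorded "until 4 weeks after he or she has completed or discontinued the investigational product must be recorded in the subject's eCRF".

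**General duty to report.** Section 8.3.2 opens differently: "Partner of a subject who become pregnant at any time while the subject is taking part in the study must be reported". It does not say whether the 4-week limit applies to the date of conception or the date of notification.

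**Contraception period.** Section 4.2.1 (and the synopsis) requires contraception "during the study and for 3 months after end of study or early termination".

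**When the study ends.** Section 3.2 lists "Follow-up visits at 1 week and 4 weeks after cessation of study medication" as the last element of participation. Section 5.3.8 puts the End of Study visit at Day 56 (Cohorts 1 and 2) or Day 112 (Cohort 3), ±7 days. After early withdrawal, section 7.3 says: "In case a premature discontinuation this EoS visit should occur within the next two weeks after the last dosing".

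**Other routes.** Section 8.1 lets the post-drug AE period be extended on strong suspicion that drug remains. Section 8.4 requires related SAEs to be reported after the study if the investigator becomes aware of them. Section 8.3.2 classes pregnancy complications, spontaneous abortion and medically indicated termination as SAEs, but not pregnancy itself.

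**SAP.** Section 11.4.2 mentions pregnancy tests only for female patients, whom the protocol does not enrol. The SAP says nothing about partner pregnancies.

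**The concern.** Only men are enrolled, so partner pregnancies are the only pregnancy exposure this trial can observe. The protocol asks subjects to avoid conception for 3 months after the study, yet its collection of partner pregnancies stops at about the point where those 3 months begin. A conception in that time, or one first recognised then, meets no scheduled contact and no instruction to tell the site. An uncomplicated pregnancy is neither an AE nor an SAE under 8.3.2, so no safety-reporting rule picks it up either.

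What is at stake is the completeness of a small but irreplaceable piece of safety information. The follow-up that 8.3.2 prescribes, to 6–8 weeks past the estimated delivery date, applies only to pregnancies that reach the site in the first place. No primary or secondary endpoint depends on it.

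**Working it through.** The documents state no figure to reproduce. The check is a count of days after the last dose.

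**Inputs**
- Collection ends at day 28 after the last dose (8.3.2, 8.4).
- For completers, End of Study is nominally 28 days after the end of treatment (Day 56 − Day 28, or Day 112 − Day 84). With the ±7-day window it falls at 21 to 35 days (5.3.8). The last dose is assumed to fall on the nominal day.
- For early terminators, the 3 months are assumed to start either at the last dose (0 days) or at a final visit 14 days later, the latest that 7.3 allows.
- The protocol does not express 3 months in days. It is taken as 84 (12 weeks), 90, or 91.3 days (calendar months).

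**Formulas**

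Contraception end E = (last dose to end of study) + 3 months.

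Uncollected days U = E − 28.

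Uncollected share = U / E.

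**Results** (3 months = 84 / 90 / 91.3 days)

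| Case | Last dose to end of study | E, days | U, days | Share, % |
|---|---|---|---|---|
| Completer, earliest visit | 21 | 105 / 111 / 112.3 | 77 / 83 / 84.3 | 73.3 / 74.8 / 75.1 |
| Completer, nominal | 28 | 112 / 118 / 119.3 | 84 / 90 / 91.3 | 75.0 / 76.3 / 76.5 |
| Completer, latest visit | 35 | 119 / 125 / 126.3 | 91 / 97 / 98.3 | 76.5 / 77.6 / 77.8 |
| Early terminator, visit at day 14 | 14 | 98 / 104 / 105.3 | 70 / 76 / 77.3 | 71.4 / 73.1 / 73.4 |
| Early terminator, counted from last dose | 0 | 84 / 90 / 91.3 | 56 / 62 / 63.3 | 66.7 / 68.9 / 69.3 |

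The ranges are 73.3–77.8% for completers and 66.7–73.4% for early terminators.

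**Residual metabolite at day 28.** Protocol section 5.4.8 gives a half-life of 90 to 110 h for the N-glucuronide. At 28 days (672 h), 0.5^(672/90) = 0.6% and 0.5^(672/110) = 1.4% remain.

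**Expected yield, on an outside assumption.** At the largest gap, 36 × 98 / 365 = 9.7 person-years. If contraceptive failure were 1–5% a year and every partner could conceive (neither is in the documents), that gives about 0.1 to 0.5 pregnancies.

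**The case against.** The strongest reply is that nothing contradicts. One section sets how long subjects use contraception and the other how long data are collected. Both can be followed, and a contraception margin longer than the reporting period may be deliberate. That stands: a reader might infer that the two rules conflict, and they do not. The protocol gives no reason for the shorter collection period, however, and the shortfall in capture remains.

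A reader might also infer that the 3 months are a risk period in which events go unrecorded and SAEs are lost. The documents do not support this. The protocol never calls it a risk period, and the metabolite has fallen to about 1% by day 28. Related SAEs that the investigator learns of stay reportable under 8.4, and 8.1 permits an extension. These routes depend on chance knowledge or discretion, and none reaches an uncomplicated pregnancy. The supportable statement is that collection is not systematic.

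A third tempting inference is that a pregnancy disclosed at an End of Study visit 35 days after the last dose is already outside the collection period. The opening sentence of 8.3.2 arguably covers it, because that subject is still taking part. For completers, that sentence and the 4-week limit differ only by the visit window. For an early terminator whose last visit is at day 14, they differ by up to 14 days (28 − 14), which is a reason to reconcile the wording.

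Two further points stand. A share of calendar days is not a share of missed pregnancies, and the expected number of events is small. The consent pages are not available, so whether subjects are asked there to report later pregnancies cannot be checked.

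**Conclusion.** The point holds as a gap in systematic safety capture. As written, new partner pregnancies are not systematically collected for roughly 73–78% of the post-treatment contraception period in completers and about 67–73% in early terminators. The ranges rest on how 3 months is converted to days, on a last dose taken on the nominal day, and on where early termination is counted from. Three quarters is therefore fair for completers and slightly high for early terminators.

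The size of any paternal-exposure risk is not established by the documents, and few events are expected with 36 men. The case for changing the text is that the information can come from no other source in this trial and the change is cheap. Nothing here says that either the 3 months or the 4 weeks is the right length.

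**What to change.** 1. In protocol section 8.3.2, define the partner-pregnancy collection period as matching whatever contraception period section 4.2.1 keeps, in place of the tie to AE collection in 8.4. The AE period itself need not change.
2. Reconcile the opening sentence of 8.3.2 with that period, and state whether the limit refers to conception or to notification.
3. At the End of Study or early termination visit, instruct subjects to notify the site of a partner pregnancy until that period ends.

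If the 3 months are kept, collection for a nominal completer would run to 112–119 days after the last dose instead of 28, and the uncollected share would fall to zero. The cost is a small protocol amendment, one instruction at an existing visit, and a passive notification channel that the site keeps open about 3 months longer. No visit, sample or call is added.

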8.4. Time Period, and Frequency of Detecting AEs and SAEs

All AEs and SAEs occurring from the time a subject consents to participate in the study until 4 weeks after he or she has completed or discontinued the investigational product must be recorded in the subject's eCRF. Importantly, SAEs will have to be reported to ABIVAX or its designee within 24 hours of awareness of an SAE.

Legislative guidance requires also reporting any **related** SAEs to be reported after the subject finished the study if the investigator becomes aware of them.

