7. SUBJECT COMPLETION AND WITHDRAWAL

7.1. Subject Completion

Treatment with ABX464 shall continue until Day 28 (Cohort 1&2) or Day 84 (Cohort 3), except if a subject fulfils a premature discontinuation criterion (defined below). After discontinuation of study product (End of Rx Visit; Day 28/84) subjects will return for two follow-up visits (FU Visit; Day 35/91 and EoS Visit; Day 56/112).

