8.1. Definition of an AE

Any untoward medical occurrence in a subject or clinical investigation subject administered a pharmaceutical product and which does not necessarily have to have a causal relationship with this treatment.

An AE can therefore be any unfavorable and unintended sign (including an abnormal laboratory finding), symptom, or disease (new or exacerbated) temporally associated with the use of a medicinal product, whether or not considered related to the medicinal product.

Note: The official definition also extends to AEs occurring in the placebo arm. Because of regulatory requirements, events occurring during pre-and post-treatment periods will also be designated as AEs. Therefore, reporting of such events, AEs and SAEs, will commence when the subject is enrolled into the study (date of signature of the informed consent) up until 4 weeks after the end of the treatment visits. The period after discontinuing study drug may be extended if there is a strong suspicion that the drug has not yet been eliminated.

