8.5. Recording AEs and SAEs

Severity of AEs will be assessed according to "Division of AIDS table for grading the severity of adult and pediatric adverse events", version 2.0 of November 2014.

Subjects will be asked to report all AEs as part of the procedures performed at each study visit. The site personnel will document all AEs in the subject's medical record. All AEs subsequently must be recorded in the appropriate eCRF sections.

The following points must be recorded for each event:

- A description of the event in medical terms, not as reported by the subject;
- Date of onset (start date);
- Date of resolution (stop date);
- The time of onset with respect to administering the investigational product;
- The severity of the sign/symptom or clinically significant abnormal laboratory value according to CTC AE Classification;
- The causal relationship between the investigational product and the occurrence of each AE. This will be assessed by each investigator using clinical judgment. Alternative causes, such as natural history of the underlying diseases, concomitant medications, other risk factors and the temporal relationship of the event to the investigational product will have to be considered. The causality of all AEs should be assessed by the investigator with the following question: Is there a reasonable possibility that the AE may have been caused by the investigational product? And answered "NO" (if not related) and "YES" (if related);
- Action taken regarding the investigational product:
 - No action;
 - Temporary discontinuation;
 - Permanent discontinuation;
- Subject's outcome:
 - Recovered without sequelae / resolved without sequelae;
 - Recovered with sequelae / resolved with sequelae;
 - Recovering/Resolving;
 - On-going;
 - Fatal (for SAEs only).

If in any one subject, the same AE occurs on several occasions, the AE in question must be documented and assessed anew each time.

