8.6. Reporting of SAEs to ABIVAX or its designee

Throughout the study, the reporting of SAEs to the Sponsor or its designee will be done through the SAE forms in the eCRF. In case the electronic SAE reporting system does not work, or after freezing of the subject's eCRF, paper SAE report forms should be used which will be faxed to ABIVAX or its designee.

It is the investigator's responsibility to ensure that the SAE report is submitted to ABIVAX or its designee, within **24 hours after knowledge of the event(s)**. The SAE forms or paper report forms should be completed as thoroughly as possible, with all the available details of the event and signed by the investigator or designee. An assessment of causality should always be provided at the time of the initial report. If the investigator or designee does not have all information regarding the SAE, he/she should not wait to receive additional information before completing the form and notifying ABIVAX or its designee.

Additional or follow-up information relating to the initial SAE report, will be requested, if necessary. Again, this information is to be completed and submitted through the SAE forms within 24 hours of receipt of the information. If the paper SAE report form was used due to technical constraints (see above), the SAE forms in the eCRF should be updated once the system is functional again (and not later than 24 hrs. afterwards), prior to using it to report any additional information. Furthermore, when additional information is received on an SAE after freezing of the subject's eCRF, new or updated information is to be recorded on a paper SAE report form with all the changes signed and dated by the investigator.

In the rare occasion when the electronic system for reporting SAEs does not work and in the absence of facsimile equipment, the investigator should notify ABIVAX or its designee by telephone within the given timeframe, and send a copy of the SAE report form by mail or email.

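### In Cohorts 1 and 3 the last biopsies are taken at the last planned visit, so 24 of 108 planned sigmoidoscopies have no later enquiry about complications

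*Protocol*

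**What the plan says.** Protocol section 5.3.8 lists, at the End of Study visit, "Flexible sigmoidoscopy with collection of rectal biopsies (Cohort 1 and 3 only"). Section 5.4.6 plans 15 to 20 biopsies per procedure, and Table 6 allocates 18 for HIV-positive subjects. Section 7.1 makes this the last planned contact: after treatment, "subjects will return for two follow-up visits (FU Visit; Day 35/91 and EoS Visit; Day 56/112").

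Adverse events are recorded "until 4 weeks after he or she has completed or discontinued the investigational product" (section 8.4). Section 8.1 gives essentially the same end date, "up until 4 weeks after the end of the treatment visits", with an extension only for suspected residual drug. On how events are found, section 8.5 states: "Subjects will be asked to report all AEs as part of the procedures performed at each study visit".

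After the study a narrower route remains. Section 8.4 requires related "SAEs to be reported after the subject finished the study if the investigator becomes aware of them", and under section 8.6, "after freezing of the subject's eCRF, paper SAE report forms should be used". The causality question in section 8.5 concerns the drug alone: "Is there a reasonable possibility that the AE may have been caused by the investigational product". Section 8 does recognise events related to procedures, but only for the screening period.

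**The concern.** Some biopsy complications appear hours or days after the subject has gone home. For the End of Study biopsies, nobody is due to ask about them. The gap falls mainly on non-serious events, which need not be recorded once the window has closed, and on serious events that the site never hears of.

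The passive route does not clearly cover this case. Section 8.4 does not say whether a serious event caused by a study procedure counts as related. An investigator answering the drug-only causality question could properly answer no for a biopsy bleed. The subject diary (section 6.3.1) allows side effects to be noted, but no return of it after the last visit is described.

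At stake are the safety of volunteers who undergo research-only biopsies and the completeness of the overall adverse event summary.

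**Working it through.** The plan states no number of procedures, so there is no figure to reproduce. The count comes from the visit lists in protocol sections 5.3.2 to 5.3.8, with 12 subjects per cohort (section 3.1.1).

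**Procedures and the next listed adverse event assessment**

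| Cohort | Sigmoidoscopy days | Procedures | Days to next assessment |
|---|---|---|---|
| 1 | 1, 28, 56 | 12 × 3 = 36 | 27, 7, none |
| 2 | 1, 28 | 12 × 2 = 24 | 6, 7 |
| 3 | 1, 28, 84, 112 | 12 × 4 = 48 | 27, 28, 7, none |

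- Total: 36 + 24 + 48 = 108.
- Next assessment at 6 to 7 days: 12 + 24 + 12 = 48.
- Next assessment at 27 to 28 days: 12 + 24 = 36.
- No later assessment: 12 + 12 = 24, so 24/108 = 22%. The remainder is 48 + 36 = 84.
- Biopsies at those 24 procedures: 24 × 15 = 360 to 24 × 20 = 480 (432 at the 18 of Table 6).

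**Recording window left after the last biopsy**

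Days left = (last treatment day + 28) − End of Study day. The visit has a ±7-day window.

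- Early limit (Day 49 or 105): 7 days left.
- Nominal day: 28 + 28 − 56 = 0 and 84 + 28 − 112 = 0.
- Late limit (Day 63 or 119): the window closed 7 days before the biopsy.
- Early leavers have the visit within two weeks of last dosing, with sigmoidoscopy subject to willingness (section 7.3). At least 28 − 14 = 14 days remain.

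No contact is planned in any of these cases.

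**Sensitivity of the count**

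- Section 5.4.6, read literally, adds a Day 56 procedure in Cohort 3, which the visit list in 5.3.5 does not have. That gives 24/120 = 20%.
- SAP section 3.1 does not exclude Cohort 2 from the last tissue sample, which would give 36/120 = 30%. Protocol 5.3.8 limits that biopsy to Cohorts 1 and 3, so 22% is the better figure.
- All counts assume 36 completers; replacements would add procedures.

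**Illustration under assumed rates**

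The documents give no complication rate. If each procedure carried an independent probability p of a delayed complication, the chance of at least one in 24 is 1 − (1 − p)^24:

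| Assumed p | Chance of at least one |
|---|---|
| 0.1% | 2.4% |
| 0.5% | 11.3% |
| 1% | 21.4% |
| 2% | 38.4% |

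**The case against.** The best reply is that little follows from the gap. Section 5.4.6 reports a low adverse event rate over more than 1,000 procedures. Drugs that raise bleeding risk are prohibited for the whole study (section 6.8.2), and mucosal abnormality and significant gastrointestinal bleeding are exclusions (section 4.2.2). An adverse event assessment is listed at the End of Study visit, so same-day events are captured. The visit falls 28 days (672 h) after the last dose, about 6 to 7.5 half-lives of the metabolite at 90 to 110 h, so events then would say little about ABX464. All of this stands, and it keeps the point minor. But the exclusions and prohibitions lower risk; they do not detect events.

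Three narrower objections also have some force:

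- Section 8.5 says subjects are asked at each visit, not only at visits. Even so, no other enquiry is described. Consent pages and part of the flow-chart notes are not available, and discharge advice may appear there. Advice would still not be a planned enquiry.
- Of the 84 procedures counted as followed up, 36 wait about 4 weeks for the next assessment. That is a weak check, but those subjects are eventually asked within the recording period.
- The 7-day interval for a call has no source in the documents. It is a judgement, although it matches the trial's own spacing between the end-of-treatment biopsies and the follow-up visit (Day 28 to 35, Day 84 to 91).

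**Conclusion.** The concern holds, as a minor point. For 24 of 108 planned procedures (22%; 20% if section 5.4.6 is read literally), all at the End of Study visit in Cohorts 1 and 3, no enquiry about delayed complications is planned. On the nominal schedule the recording period ends the same day.

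The number of events missed is unknown and probably small. Under SAP section 11.4.1 treatment-emergent events stop at the end of treatment, so those tables and the conclusions about ABX464 do not change. What is incomplete is the overall adverse event summary, which runs to the End of Study visit (protocol 9.3) or the end of the study (SAP 11.4.1), and the protection of subjects after their last biopsies.

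SAP section 8 shows that Cohort 1 had already reached Day 56. From then on, the change could reach at most 12 Cohort 3 subjects: 12 of 48 Cohort 3 procedures (25%), or 12 × 15 = 180 to 12 × 20 = 240 biopsies.

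**What to change.** - In protocol sections 8.1, 8.4 and 5.3.8, end adverse event recording at the later of 4 weeks after the last dose and about 7 days after the last sigmoidoscopy.
- Add one telephone call by existing site staff about 7 days after that sigmoidoscopy. Early leavers who have the procedure should also get the call, although their recording window is already open.
- State in section 8.4 that related serious events reportable after the study include those related to study procedures.
- Run the overall adverse event summary in protocol 9.3 and SAP 11.4.1 to the same date.
- Make the conforming edits: the pregnancy-reporting sentence in section 8.3.2, which is tied to the section 8.4 window, the flow chart, section 7.1 and the visit table in SAP 3.4.
- Apply this to every Cohort 1 or 3 subject whose End of Study biopsy is still to come.

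The cost is a protocol amendment with ethics submission, a SAP edit, an eCRF entry for the call, and one call per subject: 24 if adopted from the start, at most 12 once the SAP was written. No extra visit, procedure, sample or staff is needed. Each subject's eCRF would close about a week later.
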